15.5 Analysis of Safety Endpoints

All reported SAEs and AEs will be coded using MedDRA and grouped by body system. SAEs and AEs will be tabulated by treatment group using standard coding terms sorted by body system. The incidence of AEs in each treatment arm will be tabulated by seriousness, severity, and relationship to study drug. If an AE is reported more than once during the study period for a given subject, the greatest severity and the worst-case relationship will be presented in tables. The number of SAEs and AEs will be summarized for each treatment group as follows: (i) The proportion of subjects with at least one (S)AE, (ii) The average number of (S)AEs per patient, and (iii) The rate of (S)AEs per patient week of follow-up. Histograms showing the frequency of the number of (S)AEs in each treatment group will be included. Rates of (S)AEs by System Organ Class (SOC) will be presented by treatment group. Poisson regression modeling will be used to derive rate ratios and 95% CIs for each SOC. The rate ratios will be compared using a two-sided 0.05 level test for Poisson count data.

Safety lab data at each study visit and changes from baseline will be summarized by treatment group. In addition, the following clinical laboratory summaries will be presented by treatment group: (i) the incidence of clinically significant abnormalities at each study visit; and (ii) tables summarizing the frequencies of subjects below, within, and above the normal reference ranges at baseline and end of study; and (iii) tables displaying baseline to end of study shifts in each laboratory value (shifts between below, within or above normal range).

The proportion of subjects permanently discontinuing study drug will be tabulated by treatment group. Drug discontinuation events will be categorized as: (1) Permanently discontinued study drug and (2) Permanently discontinued study drug and withdrew from study. The reason for permanent drug discontinuation will be summarized.

The number of hospitalization events and proportion of subjects hospitalized from baseline to Day 56 will be summarized and compared by treatment group. Poisson regression modeling will be used to derive rate ratios and 95% CIs to compare hospitalization rates between treatment groups.

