Clinical experience in CF. We completed a Phase 1b non-randomized safety and pharmacokinetic (PK) trial in CF adults. The study involved two different dosing cohorts, 100 mg/m²/day and 200 mg/m²/day infused for a total of 5 days. The first dosing cohort included 9 CF subjects (4 males and 5 females) and the second included 11 CF subjects (6 males and 5 females). The mean baseline forced expiratory volume in one second (FEV₁) and forced vital capacity (FVC) were 2.25 liters (L) (range 1.06 to 4.59 L) and 3.60 L (range 1.84 to 6.11 L). The mean body mass index was 22.7 kg/m² (range 17.3 to 31.2 kg/m²) thus representing a broad

Version 2.0 Version Date: 28 AUG 14 Page 15 of 57

spectrum of disease in CF adults. No serious adverse experiences (SAEs) were noted in the study. There were a total of 41 adverse events (AEs); 8 were deemed possibly related, one definitely related and 32 unrelated to study agent. Of the 9 AEs that were deemed related, 8 were categorized as mild and one was categorized as moderate severity. The AE categorized as definitely related to the study was bruising at the site of an intravenous line site (related to study procedure, not study drug). The other AEs included headache, dizziness, chest pain, gastroesophogeal reflux disease, increased sputum production, migraine headache, increased lethargy, gastrointestinal bloating and elevated blood glucose. Of the 41 AEs, 39 were deemed mild in severity with one moderate and one severe in severity. The severe AE was a headache. No AE led to a treatment discontinuation. The primary safety concern of IV gallium is renal toxicity. No evidence was found of renal injury during and after infusion using serum creatinine, blood urea nitrogen (BUN) and urine albumin/creatinine ratio. We found no evidence of perturbation of calcium homeostasis as noted by blood ionized calcium levels. Overall, the drug appeared safe and well tolerated in CF.

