15 STATISTICAL METHODS AND CONSIDERATIONS

Prior to the analysis of the final study data, a detailed SAP will be written describing all analyses that will be performed. The SAP will contain any modifications to the analysis plan described below. Except where otherwise noted, all tests will be two-sided and statistical significance will be determined at the 0.05 level.

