15.7 Sample Size and Randomization

The primary endpoint is the difference between treatment groups in the proportion of subjects with a 5% or greater improvement in the relative change in FEV₁ in liters from baseline to Day 28. A 5% or greater improvement in the relative change is well established as a minimum clinically important change by CF physicians based on the choice of the non-inferiority margin of 4% in a recent Phase 3 clinical trial (46) and the effect size of a number of key therapies utilized in CF (43:47-52). A responder-based endpoint is also an established approach for identifying efficacy on an individual patient level, as opposed to highly variable average changes across patients within a treatment group. In the recently completed pilot study of gallium, 8 of 11 (73%) experienced a 5% or greater relative change in FEV₁ from baseline to Day 14 and 5 of 11 (45%) experienced a 5% or greater relative change in FEV₁ from baseline to Day 28. There was no placebo group in the study; however, data from a completed randomized trial of azithromycin in subjects chronically infected with P. aeruginosa was used to estimate the expected responder rate among those receiving placebo (43). In this study, the proportion of placebo subjects with a 5% or greater relative improvement in FEV₁ ranged from 28% to 33% across study visits from Day 28 through Day 84. Thus, the expected treatment difference in this study is between approximately 15% and 45% based on the observed response rates from the gallium pilot study. However, it is felt that the minimum clinically important difference between groups is based on clinician opinion is 30% given the treatment burden of an intravenous therapy (e.g., increasing the responder rate from 30% to 60%). With a sample size of 60 per group and assuming a responder rate of 30% in the placebo group, the study has 90% power to detect a 28.3% or greater improvement in the responder rate. Accounting for an attrition rate of 10% and interim analyses, the study will still have 90% power to detect a treatment difference of 30.0% or greater between groups.

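### Section 15.5 makes no allowance for extra-Poisson variation in AE rates by SOC and hospitalization rates; if events cluster within subjects, intervals and tests for the common SOCs will be too liberal

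*Protocol*

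**What the plan says.** Protocol section 15.5 summarizes AEs and SAEs in three ways, the third being "iii) The rate of (S)AEs per patient week of follow-up". That summary counts repeat events in the same subject. For inference by System Organ Class it states: "Poisson regression modeling will be used to derive rate ratios and 95% CIs for each SOC". It adds: "The rate ratios will be compared using a two-sided 0.05 level test for Poisson count data".

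For hospitalizations it says: "Poisson regression modeling will be used to derive rate ratios and 95% CIs to compare hospitalization rates between treatment groups". No test is named for these beyond the general rule in section 15 that "all tests will be two-sided and statistical significance will be determined at the 0.05 level".

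The protocol mentions no scale parameter, robust variance, negative binomial model or other allowance for overdispersion. Section 15.5 does also plan the proportion of subjects with at least one (S)AE, the proportion hospitalized, and histograms of the number of (S)AEs per subject. Section 15 allows the SAP to modify the plan.

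**The concern.** A Poisson model takes the variance of a subject's event count to equal its mean. That fails when subjects differ in their underlying rate, or when one clinical episode is recorded as several events.

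Both are plausible here:

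- Section 6.2 admits adults from 25% of predicted FEV1 upward with no upper limit.
- Sections 9.1.4 and 9.2 require new clinically significant examination and laboratory abnormalities to be recorded as AEs.
- The chemistry panel in section 9.2.2 contains linked analytes (AST, ALT and GGT; BUN and creatinine; calcium and ionized calcium), so one episode can yield several AEs.

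If the variance exceeds the mean, the standard errors are too small. Some SOCs would then show an apparent harm or an apparent benefit more often than the stated 5%. Safety is the first-listed secondary objective in section 3.2, so the SOC rate table will be read closely.

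**Working it through.** **Inputs from the protocol.** There are 60 subjects per arm (section 15.7) and the SOC test is two-sided at 0.05 (section 15.5). The pilot reported 41 AEs in 9 + 11 = 20 subjects (section 1.2), which is 41/20 = 2.05 per subject over all SOCs together, and no SAEs.

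**Assumed inputs.** The documents give no between-subject variance and no expected rate for any SOC. Both are therefore varied: mean events per subject in one SOC, m = 0.1, 0.2, 0.5 and 1; negative binomial dispersion k = 0.25, 0.5 and 1.

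**Step 1: the stated level when the Poisson assumption holds.** With arm totals A and B and equal follow-up, the log rate ratio has standard error sqrt(1/A + 1/B), and the asymptotic level is 0.050. In 100,000 simulated trials with k = 0, the Wald test rejected in 4.8% at m = 1 and 4.8% at m = 0.5. So the plan's 0.05 is right under its own model.

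**Step 2: the level under overdispersion.** With variance m + k·m², the variance-to-mean ratio is φ = 1 + k·m. The Poisson standard error is too small by a factor sqrt(φ), and the true level is approximately 2·(1 − Φ(1.96/sqrt(φ))). Example: m = 1, k = 0.5 gives φ = 1.5, sqrt(φ) = 1.225, 1.96/1.225 = 1.600, and a level of 0.110.

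Each cell lists the values for k = 0.25 / 0.5 / 1, with 100,000 simulated trials per setting:

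| Mean per subject | Closed form | Simulated Wald | Simulated exact conditional | 95% CI coverage (Wald) |
|---|---|---|---|---|
| 1.0 | 0.080 / 0.110 / 0.166 | 0.077 / 0.109 / 0.163 | 0.066 / 0.095 / 0.146 | 92% / 89% / 84% |
| 0.5 | 0.065 / 0.080 / 0.110 | 0.061 / 0.076 / 0.104 | 0.049 / 0.062 / 0.087 | 94% / 92% / 90% |
| 0.2 | 0.056 / 0.062 / 0.074 | 0.048 / 0.054 / 0.065 | 0.033 / 0.038 / 0.047 | 95% / 95% / 94% |
| 0.1 | 0.053 / 0.056 / 0.062 | 0.029 / 0.031 / 0.033 | 0.026 / 0.029 / 0.030 | 97% / 97% / 97% |

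The inflation fades as the SOC becomes rarer, because φ tends to 1 as m falls. At very low counts the tests are conservative in any case.

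**Step 3: several AEs from one episode.** Suppose a share p of episodes yields two AEs in the same SOC and there is no other heterogeneity. Then φ = (1 + 3p)/(1 + p), which does not shrink with the mean: 1.40 at p = 0.25 and 1.67 at p = 0.5. The simulated Wald level is about 9% and 12% at m = 0.2, and about 6% and 7% at m = 0.1. These shares are also assumptions.

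**Step 4: the remedy.** In the Step 2 settings with m = 0.5 and 1, sandwich standard errors gave levels of 0.050 to 0.056 and Pearson-scaled standard errors 0.047 to 0.050. With k = 0 and the same means, sandwich gave 0.050 to 0.051 and Pearson-scaled 0.047 to 0.048, so little is lost when there is no overdispersion. At m = 0.1 to 0.2 both were at or below nominal (sandwich 0.029 to 0.049, Pearson-scaled 0.024 to 0.042).

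**The case against.** The strongest reply is that section 15.5 names a model family and not a variance estimator. Poisson regression can be fitted with robust or scaled standard errors, and that choice is often left to the SAP. This has some force, and the repair could indeed be made there. But for the SOC comparison the protocol goes further and specifies a test for Poisson counts, so it states a method rather than staying silent.

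The second reply is that nothing in the documents shows overdispersion. That is correct. Entry also requires 14 days of clinical stability (section 6.2) and no acute antibiotics in the preceding 14 days (section 6.3), which may narrow the differences between subjects. The consequence must therefore be stated conditionally.

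The third concerns size. A reader might take the pilot mean of 2.05 AEs per subject and infer a level of 11 to 26%, which is what k = 0.25 to 1 gives at that mean. The documents do not support this reading: 2.05 is the total over all SOCs, whereas Poisson tests are planned only within each SOC. A reader might also infer that every SOC test and the hospitalization comparison are anticonservative. The rows for 0.1 and 0.2 events per subject contradict that for heterogeneity alone.

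For hospitalizations, section 15.5 plans intervals without naming a Poisson test. An inpatient hospitalization is an SAE by section 11.2, and the pilot had none in 20 subjects. The exact 95% upper limit is 3.69/20 = 0.18 per subject over the pilot's follow-up, whose length is not stated. If rates here are similar, inflation from heterogeneity would be small.

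Finally, the planned proportions do not rest on the Poisson variance, and the histograms will show the spread of counts. Both stand as partial safeguards, but neither corrects the rate ratios, their intervals or their tests.

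**Conclusion.** The point holds in a conditional and limited form. Section 15.5 prescribes Poisson inference for repeat-event counts without allowing for variance above the mean. If events cluster within subjects, intervals for the common SOCs will be too narrow and their tests will exceed 0.05. With k assumed between 0.25 and 1, the level is about 6 to 11% at 0.5 events per subject and 8 to 17% at 1; an exact conditional Poisson test reduces this but does not remove it. For sparse SOCs the level is near or below nominal, unless single episodes often generate several AEs. Hospitalizations share the gap in method but may be too few for it to matter. The primary endpoint and the subject-level safety proportions are unaffected. All sizes rest on assumed dispersion and assumed SOC rates; only the sample size, the stated level and the pilot totals come from the protocol. The change is worth making because a valid alternative costs almost nothing.

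**What to change.** In section 15.5, keep the log-linear rate model and state a log follow-up-time offset. Base all intervals and tests for SOC rates, and the hospitalization intervals, on robust (sandwich) or Pearson-scaled standard errors, and replace the reference to a test for Poisson counts accordingly. For sparse SOCs, use an exact comparison of the proportion of subjects with at least one event, with the event-count threshold set in advance.

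This takes a sentence or two in section 15.5 or the SAP and no new data. The price is somewhat wider intervals when counts are overdispersed: by a factor sqrt(φ) on the log scale, for example 1.22 at φ = 1.5.

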2.2 Risk / Benefit Assessment

No published studies exist that evaluate the safety of IV gallium nitrate in CF patients. However, there is extensive published information on the use of this compound over a wide range of doses both above and below the doses proposed in this trial in patients with both neoplastic as well as benign metabolic diseases. Moreover, this human experience extends over a period of more than 30 years, including a post-marketing experience of 17 years duration. Thus, the risks of the drug have been broadly described in thousands of patients and unique risks associated with the proposed dosing in CF patients would appear to be low. In this trial, we propose to limit our trial to stable CF subjects with normal renal function at a dose previously tested and shown to be safe in our Phase 1b CF study. Because of this, we anticipate potentially severe systemic adverse reactions to be unlikely.

A specific minimum human toxic dose has not been established. However, a "no effect" (placebo) dose of 0.05 mg/kg administered once per day subcutaneously was used in the randomized Phase 2 study in Paget's disease. A higher dose (0.5 mg/kg/d) demonstrated biological activity against markers of Paget's disease activity, but demonstrated no significant AEs. The lethal dose 50 (LD50) of gallium nitrate in mice is 4,360 mg/kg for oral doses and 600 mg/kg for subcutaneous doses (32). Renal toxicity is dose dependent and is usually the dose limiting adverse effect of parenteral gallium nitrate when administered by bolus injection or short (2 hours) IV infusion (2). Elevation of serum BUN and creatinine levels has been observed in approximately 12.5% of patients receiving recommended therapeutic doses of IV gallium nitrate (~ 400 mg/day for a typical adult). Toxicity depends on several factors: the total dose, the rate of administration, the underlying pathology, and use with other nephrotoxic drugs. Doses up to 1400 mg/m² by short IV infusion have been used in clinical trials. No significant toxicity has been observed at doses of 50 mg/m² (~ 100 mg for a typical adult) or less (33).

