5.2 Secondary Endpoints

- Difference between treatment groups in safety parameters including the incidence of AEs, changes in clinical safety labs, and hospitalizations through the end of follow-up
- Difference between treatment groups in the change in pulmonary function parameters from baseline through end of follow-up including relative change in FEV₁ (liters), absolute change in FEV₁ (liters) and in FEV₁ % predicted, and change in FVC (liters and % predicted)
- Difference between treatment groups in the change in sputum *P. aeruginosa* density based on quantitative cultures from baseline through end of follow-up
- Difference between treatment groups in the emergence of other CF pathogens, including gallium-resistant *P. aeruginosa*, from baseline through end of follow-up
- Difference between treatment groups in the change in the CFRSD-CRISS from baseline through end of follow-up
- Determination of the steady state concentration (Css) and elimination half life $(t_{1/2\beta})$ in those subjects receiving IV gallium
- Difference between treatment groups in the change in blood inflammatory markers from baseline through end of follow-up
- Difference between treatment groups in the rate of antibiotic usage including IV, oral, and inhaled for an acute indication from baseline through end of follow-up
- Longitudinal trends in clinical features and CF pathogens following treatment through the CF Foundation National Patient Registry

Version 2.0 Version Date: 28 AUG 14 Page 22 of 57

Protocol Number: GALLIUM-IP-13 Confidential

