9.2 Clinical Laboratory Measurements

After initiation of Study Drug, new clinically significant abnormal laboratory findings must be documented as an AE.

The collection of blood samples may occur via the study drug administration access point if study drug is not being administered. If study drug is being administered, blood collection must occur at a different access point.

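### Section 5.2 defines safety laboratory change as a between-group difference, but section 15.5 gives it no treatment difference or confidence interval

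*Protocol*

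**What the plan says.** The first secondary endpoint in Protocol section 5.2, repeated in the synopsis, is: "Difference between treatment groups in safety parameters including the incidence of AEs, changes in clinical safety labs, and hospitalizations through the end of follow-up". It has three components, all framed as a difference between groups.

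Section 15.5 sets out how each is analysed:

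- **Adverse events.** "Poisson regression modeling will be used to derive rate ratios and 95% CIs for each SOC", with each ratio tested two-sided at the 0.05 level.
- **Hospitalizations.** Counts and proportions are compared by arm, with Poisson rate ratios and 95% confidence intervals.
- **Laboratory values.** "Safety lab data at each study visit and changes from baseline will be summarized by treatment group". Three further by-arm displays are listed: how often abnormalities judged clinically significant occur, visit by visit; frequencies below, within and above the reference range; and shift tables. The last two run from baseline to end of study.

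On the hazard itself, section 1.2 states: "The primary safety concern of IV gallium is renal toxicity". Section 2.2 adds: "Elevation of serum BUN and creatinine levels has been observed in approximately 12.5% of patients receiving recommended therapeutic doses of IV gallium nitrate". It also describes hypocalcemia as a known effect of gallium. Section 9.2 links laboratory findings to adverse events: "After initiation of Study Drug, new clinically significant abnormal laboratory findings must be documented as an AE".

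**The concern.** The method fixed for laboratory change falls short of the quantity that section 5.2 defines. Two components of the endpoint receive an estimated between-arm effect with an interval. The third receives two columns for the reader to compare by eye.

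The shortfall lies where gallium toxicity would be expected to show. The only CF experience described is a non-randomized study of 20 subjects without placebo, so the placebo arm here is what separates a drug effect on creatinine, BUN or calcium from background variation. Without an interval, the report cannot say how large an effect on those analytes the data exclude.

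**Working it through.** **Check 1: is there a laboratory contrast anywhere in the protocol?** No. Section 15.5 gives by-arm displays only. Section 15.4 applies mixed models to lung function, sputum density, symptoms and inflammatory markers, not to safety laboratory values. The protocol does state such estimates where it wants them: in section 15.4, acute antibiotic use gets differences in proportions with 95% intervals.

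**Check 2: does the adverse event route fill the gap?** In part. Under section 9.2 a new clinically significant abnormality becomes an adverse event, and section 15.5 then gives its system organ class a rate ratio with a 95% interval. Three limits remain:

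- An investigator must first judge the finding clinically significant.
- The rate ratio pools every event in the class, and related abnormalities may be coded to different classes.
- Mean change, and change below that threshold, is not estimated.

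**Check 3: do the range and shift tables fill it?** No. They compare baseline with end of study. Safety blood tests are scheduled at Days 6, 14 and 28 (sections 10.3 to 10.5) and not at Day 56 (section 10.6). A rise at Day 6 that later resolved would appear in the by-visit summaries but not in the range or shift tables.

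**Check 4: what would an estimate look like?** The protocol states no laboratory precision or power figure to reproduce, so this is illustration only.

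*Inputs.* 60 per arm (section 15.7). 54 per arm after the stated 10% attrition: 60 × 0.90 = 54. 12.5% with BUN or creatinine elevation on gallium (section 2.2, from patients on recommended therapeutic doses, not CF). Placebo rates of 0% to 5% are assumed.

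*Newcombe interval* for d = p1 − p2, with Wilson limits (l, u) for each arm:

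lower = d − √[(p1 − l1)² + (u2 − p2)²]; upper = d + √[(u1 − p1)² + (p2 − l2)²]

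12.5% of 60 is 7.5, rounded to 8. For 8/60 against 3/60, d = 0.1333 − 0.0500 = 0.0833. The Wilson limits are 0.0691 to 0.2417 and 0.0171 to 0.1370.

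- lower = 0.0833 − √(0.0642² + 0.0870²) = −0.025
- upper = 0.0833 + √(0.1083² + 0.0329²) = 0.197

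So the difference is 8.3 points (95% CI −2.5 to 19.7). In the same way, 8/60 against 1/60 gives 11.7 points (2.0 to 22.6), and 8/60 against 0/60 gives 13.3 points (4.5 to 24.2).

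*Chance that the interval lies above zero*, by summing over two independent binomials with 12.5% on gallium:

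| Assumed placebo rate | 60 per arm | 54 per arm |
|---|---|---|
| 0% | 88% | 82% |
| 1% | 73% | 66% |
| 2% | 59% | 52% |
| 3% | 46% | 41% |
| 5% | 27% | 24% |

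*Mean change.* The 95% half-width is 1.96 × SD × √(2/n): 0.36 SD at 60 per arm and 0.38 SD at 54. The protocol gives no SD for any safety analyte, so this stays in SD units. Baseline adjustment would narrow it.

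*What the existing route would show.* Suppose the same 8 and 3 events were all reported as adverse events in one class, with no other events there and equal follow-up. The rate ratio would be 8/3 = 2.67, with 95% interval exp[ln(2.67) ± 1.96 × √(1/8 + 1/3)] = 0.71 to 10.1. That is a between-arm estimate, but of reported events and not of laboratory change.

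**The case against.** The strongest case against has four parts.

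1. **Analysis detail belongs in the SAP.** Section 15 defers a detailed description of all analyses to a SAP that is not shown and may contain these contrasts. This stands in part: covariates and table layout are SAP matter. But section 15.5 is not silent on laboratory values. It states their analysis, and that analysis does not match section 5.2.

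2. **Renal toxicity does get a between-arm estimate.** This stands. A reader might infer that the drug's main hazard is never given a treatment difference or confidence interval. The documents do not support that, because clinically significant abnormalities are adverse events under section 9.2 and enter the rate ratios in section 15.5. What lacks a contrast is laboratory change itself.

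3. **The endpoint's opening words are stock.** Most items in section 5.2 open the same way. Emergence of other CF pathogens does so too, and section 15.4 gives it descriptive analyses only. The proportion of subjects with at least one adverse event is also only summarized by arm. Descriptive laboratory reporting is usual. This weakens the contradiction and keeps the point minor. It does not make the section 15.5 displays an estimate of a difference.

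4. **The illustration can be made to flatter.** The 12.5% is not from CF subjects, section 1.2 reports no evidence of renal injury in the Phase 1b study, and the placebo rates are assumed. At 60 per arm, 8% against 1% gives only a 36% chance that the interval excludes zero, and 5% against 1% gives 11%. This stands, so the figures show what an interval would look like and are not a claim of adequate power.

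**Conclusion.** The point holds and is minor. Section 5.2 defines laboratory change as a between-group difference, and section 15.5 provides no difference or interval for it, while adverse event rates and hospitalizations in the same endpoint have both. The adverse event route is a real but coarse partial substitute.

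This conclusion rests on the text of the two sections and not on the illustration. The 88% to 27% range at 60 per arm (82% to 24% at 54) depends on a non-CF gallium rate and assumed placebo rates. Even where zero is not excluded, an interval such as −2.5 to 19.7 points states how much harm remains compatible with the data, which two percentages side by side do not.

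A reader might also infer that the trial fails its safety objective. It does not: that objective is to assess safety and tolerability, and randomized by-arm summaries contribute to it. No stated figure and no primary result is affected.

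**What to change.** In section 15.5, for serum creatinine, BUN and ionized calcium only, add:

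- the between-group difference in change from baseline, adjusted for the baseline value, with a 95% confidence interval at Days 6, 14 and 28;
- the between-group difference, with a 95% confidence interval, in the proportion newly outside the normal range in the harmful direction at any post-baseline visit.

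Label these as estimation without multiplicity control, and keep all other laboratory values descriptive. Rewording section 5.2 to call laboratory change descriptive would also remove the mismatch, but would give up the estimate.

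The cost is a few lines of text and some table rows: 3 analytes × 3 visits = 9 mean differences, plus 3 differences in proportions. No new samples or visits are needed, since all three analytes are already in the section 9.2.2 chemistry panel. The downside is 12 intervals without multiplicity adjustment, which the label makes plain.
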